#### 4.4. **Patient Registration**

Data for patients enrolled on interventional trials must be entered per current practices into the Oncore electronic clinical trials management system.

University of Arizona Cancer Center

Patients must be registered prior to initiation of treatment. Patients will be registered through a Breast Team Clinical Research Coordinator (CRC) from 8:00 a.m. to 5:00 p.m., Mountain Standard Time, Monday through Friday, (excluding holidays)

University of New Mexico Cancer Center

Patients must be registered prior to initiation of treatment. Prior to registration, eligibility criteria must be confirmed with the UNM CC Clinical Research Office. If the patient meets the eligibility criteria he/she will be assigned a **unique patient study number** by the Clinical Research Office as further detailed below.

The patient will be registered in the Oncore System using the study number.

#### 4.5. **Study Patient Identification**

Patients who have been consented and are undergoing study screening will be identified on study-related documentation and forms by their initials (first/middle and last name initials). All patients treated on this trial will be identified by their study initials and a unique study identification number. A unique study number will only be assigned to patients who meet the eligibility requirements and have completed the screening visit and are registered for treatment. The unique number will begin with the following prefix: BD. The prefix will be followed by the patient identification number beginning with # 001 in each cohort. These numbers will be issued to patients sequentially and no patient identification numbers will be re-assigned in the event that the subject withdraws from protocol treatment.

Patients enrolled at University of New Mexico Cancer Center will be identified by prefix NM to help identify patients enrolled at that site. The prefix will be followed by the patient identification number beginning with # 001 in each cohort. These numbers will be issued to patients sequentially and no patient identification numbers will be re-assigned in the event that the subject withdraws from protocol treatment

## 5. **Study Procedures**

### 5.1. **Pretreatment**

Patients will be consented and evaluated for participation based on the following procedures which should be performed within 28 days of registration

- Physical exam
- Complete blood count with absolute neutrophil count and differential
- Liver function panel to include total bilirubin
- Serum Creatinine
- Staging studies by the same method that will be used throughout the study (per treating physician discretion):
  - Such as CT of the chest, abdomen and pelvis or
  - PET/CT or
  - Bone scan

### 5.2. **Patient Registration**

See section 4.4 above

#### **Registration Guidelines**

Before a subject participates in the trial, the investigator or delegate is responsible for obtaining written informed consent after adequate explanation of the aims, methods, anticipated benefits, subject responsibilities and potential hazards of the study and before any protocol-specific screening procedures or any study required medications are administered. All patients must be registered before the start of treatment.

### 5.3. **Treatment Phase**

The following tests and observations will be performed during the treatment phase of

the study.

Test	Interval
Physical exam	No less than every 8 weeks
Complete blood counts and ANC and platelet count	No less than every 4 weeks
Liver function panel to include total bilirubin	No less than every 4 weeks
Serum creatinine	No less than every 4 weeks
Repeat disease assessment with physical exam and repeat imaging test that showed measured pretreatment	No less than every 9 weeks

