**Pegylated Liposomal Doxorubicin (Doxil)**

Doxil® (doxorubicin HCl liposome injection) is doxorubicin hydrochloride (HCl) encapsulated in STEALTH® liposomes for intravenous administration. Doxorubicin is a cytotoxic anthracycline antibiotic isolated from *Streptomyces peucetius* var. *caesius*. Doxorubicin HCl, is the established name for (8S,10S)-10-[(3-amino-2,3,6-trideoxy-β-L-lyxohexopyranosyl)oxy]-8-glycolyl-7,8,9,10-tetrahydro-6,8,11-trihydroxy-1-methoxy-5,12-naphthacenedione. Doxil will be obtained from commercial sources and administered on days 1 of 21 day cycle (this will be done as standard of care). This drug will be administered as directed by their package inserts or standard of care. Doxil will be administered intravenously at 30mg/m^2.

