**Dose Modification Guidelines**

Patients will be carefully monitored for toxicity. Adverse reactions, such as Hand Foot Syndrome (HFS), hematologic toxicities, and stomatitis will be managed by dose delays and adjustments. Following the first appearance of a Grade 2 or higher adverse reactions, the dosing will be adjusted or delayed as described in the following tables. Once the dose has been reduced, it will not be increased at a later time. After a dose modification, if treatment is continued, it will return to the original dose interval of every 21 days.

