**Table 3: Dose Adjustments for Hematological Toxicity**

Situation	Doxil Dose
First episode of febrile neutropenia (grade 3 or 4)	75%
Second episode of febrile neutropenia (grade 3 or 4)	Discontinue
Grade 4 thrombocytopenia or bleeding associated with thrombocytopenia	75%

In addition to the above dose adjustments, subjects experiencing febrile neutropenia secondary to Doxil may receive G-CSF therapy in association with subsequent chemotherapy doses.

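### Blood counts are required only every 4 weeks against 21-day dosing, and the two Table 3 rows that continue treatment state a reduced dose but no hold

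*Combined protocol and SAP*

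**What the plan says.** The test schedule in section 5.3 sets the interval for "Complete blood counts and ANC and platelet count" at "No less than every 4 weeks". Section 7 (Study Drug Information) has the drug "administered on days 1 of 21 day cycle". The baseline count in section 5.1 is among the "procedures which should be performed within 28 days of registration", so it is tied to registration and not to the first dose. The neutrophil and platelet limits in 4.1.8 apply to eligibility only.

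The Dose Modification Guidelines state that "hematologic toxicities, and stomatitis will be managed by dose delays and adjustments", and that "the dosing will be adjusted or delayed as described in the following tables". In Table 3, a first febrile neutropenia and "Grade 4 thrombocytopenia or bleeding associated with thrombocytopenia" each carry the single entry 75%. A second febrile neutropenia leads to discontinuation. Tables 1 and 2 give explicit delays with a recovery grade for hand-foot syndrome and stomatitis. Table 4, for other toxicities, holds grade 4 events until they resolve, but its grade 3 row is also a bare 75%.

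**The concern.** A monitoring interval longer than the dosing interval means that some doses can be given, in full compliance with section 5.3, without a recent blood count. The dose-modification rules need to know whether a haematological toxicity is present, and cytopenias are graded from a count. The schedule therefore does not guarantee the information those rules need.

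Table 3 adds a second gap. The general text promises delays as set out in the tables, but Table 3 sets out none for the two events after which treatment continues. Read row by row, a grade 4 non-haematological toxicity has an explicit hold and grade 4 thrombocytopenia does not. What is at stake is patient safety at re-dosing.

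**Working it through.** The plan states no figure on this point, so there is none to reproduce. The check is schedule arithmetic.

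**Inputs.** Count interval 28 days (section 5.3, taken at its minimum). Dose interval 21 days (section 7). Assumptions: counts exactly 28 days apart, no dose delays, no extra counts prompted by symptoms or the label, and a last required count 0 to 27 days old at the first dose.

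**Age of the last required count.** Let *a* be its age in days at dose 1. At dose *k* + 1 the age is (*a* + 21*k*) mod 28. The greatest common divisor of 21 and 28 is 7, so any four consecutive doses have ages *r*, *r* + 7, *r* + 14 and *r* + 21 in some order, where *r* = *a* mod 7 runs from 0 to 6.

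- Same-day count: needs *r* = 0, that is *a* = 0, 7, 14 or 21. This is 4 of the 28 starting ages, each giving 1 dose in 4. The other 24 give none in 4.
- Count no more than 3 days old: needs *r* of 0 to 3. This is 16 of 28 starting ages, each giving 1 dose in 4. The other 12 give none.
- Oldest count in each run of four: *r* + 21, so 21 to 27 days.
- Mean age: *r* + 10.5, so 10.5 to 16.5 days.

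Example with a count on the first dose day: the ages at doses 1 to 4 are 0, 21, 14 and 7 days. Dose 5 falls on day 84 after the first dose, which is again a count day (84 = 4 × 21 = 3 × 28).

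**Other course lengths.** With a count on the first dose day, same-day counts fall at doses 1, 5, 9 and so on. The share is then 1 of 2, 1 of 3, 1 of 4 or 2 of 5 for courses of 2, 3, 4 or 5 doses. One in four is a limit for any run of four doses, or in the long run. It is not a limit for every patient's course.

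**Table 3 beside the other tables.**

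| Table | Event | Hold or delay stated? |
|---|---|---|
| 1 and 2 | Grade 3 or 4 hand-foot syndrome or stomatitis | Yes: up to 2 weeks or to grade 0-1 |
| 3 | First febrile neutropenia | No: 75% only |
| 3 | Grade 4 thrombocytopenia or related bleeding | No: 75% only |
| 4 | Other toxicity, grade 4 | Yes: until resolved |

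Both Table 3 rows that continue treatment lack a hold.

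**The case against.** The strongest reply is that this is left to routine care on purpose. The drug is commercial and is given under package inserts or standard of care (section 7). Patients already on it may enrol (4.1.10). The study in effect adds a BRCA1 assay to ordinary treatment. Four weeks is a floor, and sites may test every cycle. Other safeguards exist: marrow thresholds at entry (4.1.8), optional G-CSF after febrile neutropenia (text below Table 3), stopping for non-reversible grade 4 haematological abnormalities (synopsis, Duration of Intervention) and withdrawal for toxicity on the investigator's judgment (4.3).

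Much of this stands and lowers the practical risk. It does not remove the point. The reference to routine care is general and names no count, whereas section 5.3 states an explicit, looser minimum. None of the other safeguards requires a count or a hold before the next dose.

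The exact 28-day spacing is also hypothetical. That is fair: the arithmetic shows what the protocol guarantees, not what sites will do.

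A reader might infer that Table 3 tells sites to dose through an unresolved cytopenia. It does not. The tables are headed as recommended guidelines, and the text above them mentions delays for haematological toxicity. The gap is a missing instruction, not a wrong one.

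**Conclusion.** The point holds as a low-cost safety improvement. The required count interval is longer than the dosing interval, and no section requires a pre-dose count. On the protocol minimum, at most one of any four consecutive doses has a same-day required count, and one of each four rests on a required count 21 to 27 days old. This assumes exact 28-day spacing and no dose delays. The lack of a hold in two Table 3 rows is a secondary inconsistency with the guidelines' own text.

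Three stronger readings are not supported. First, one in four is not a ceiling for every patient, because short or other course lengths can give a higher share. Second, the documents do not show that any patient would be harmed, and the number affected cannot be derived from them. Third, nothing here touches the response-rate analysis or the Simon boundaries.

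**What to change.** In the section 5.3 schedule, replace the blood count interval with: *CBC with ANC and platelets before each dose*. Secondarily, in Table 3, change the two 75% entries to: *Hold until resolution, then resume at 75%*. Leave the discontinuation row and the 75% level as they are.

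This guarantees a current count at all four of any four doses and an explicit hold after the two listed events. It does not remove the reliance on routine care: the numeric recovery threshold, and the handling of neutropenia without fever (which has no row in Table 3), stay with the package insert or standard of care. The open-ended hold follows Table 4's grade 4 row. The two-week limit in Tables 1 and 2 is an alternative model.

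**Cost.** One schedule line and two table cells. Over 12 weeks, 84/21 = 4 counts replace 84/28 = 3. If time on treatment equals the 2.5-month median progression-free survival quoted in the background (about 76 days, an assumption), doses fall on days 1, 22, 43 and 64 and minimum counts on days 1, 29 and 57. That is 4 against 3, or about 50 extra routine counts for 50 patients. There are none extra where pre-dose counts are already usual. Some doses may be delayed; the documents do not allow an estimate of how many.

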#### 5.4. **Follow Up**

Patients will be followed according to the institutional standard guidelines. We will only follow patients who have experienced grade 3 or 4 adverse event or serious adverse event that are possible/probably or definitely related to the study required medication for 30 days after the week 9 visit.

#### 6. **Criteria for Evaluation**

The primary endpoint is the clinical response rate (complete response + partial response, see 6.3.4.1). Other efficacy measures are progression-free survival.

#### **Evaluation Criteria Definitions**

6.1. **Treatment related toxicity** is an adverse effect that is clearly related to the chemotherapy regimen.

6.2. **Clinical response**: Will be evaluated using the following definitions:

##### 6.2.1. **Baseline assessment**:

To assess response, it is necessary to estimate the tumor burden at baseline before the start of treatment. Subsequent measurements will be compared to this. Measurable disease is defined by the presence of at least one lesion that can be accurately measured in at least one dimension (longest diameter recorded) as  $\geq 2.0$  cm with conventional techniques or as  $\geq 1.0$  cm by spiral CT scan. All lesions that do not fit these criteria are considered to be non-measurable disease. All measurable lesions up to a maximum of five lesions per organ and ten lesions in total should be identified as target lesions and be recorded and measured at baseline. Target lesions should be selected on the basis of their size (those with longest diameter) and their suitability for accurate repeated measurements. A sum of the longest diameter for all target lesions will be calculated and reported as the baseline sum. This will be used as the reference for characterizing the objective tumor response

6.2.2. **Tumor assessments** will be made during screening and then at 9 (± 7 days) weeks to evaluate response rate. There after the use of further imaging for tumor assessment will be left to the treating physicians discretion

6.2.3. **Evaluation of target lesions**

Tumor response will be evaluated as follows (see appendix 2, Recist 1.1)

**6.2.4**  
**of best response:**  
overall  
the best  
recorded  
of  
repeat  
at 9 -12  
days)

Target lesions	Non-target lesions	New lesions	Overall response
CR	CR	No	CR
CR	Non-CR/non-PD	No	PR
CR	Not evaluated	No	PR
PR	Non-PD or not evaluated	No	PR
SD	Non-PD or not evaluated	No	SD
Not all evaluated	Non-PD	No	NE
PD	Any	Yes or no	PD
Any	PD	Yes or no	PD
Any	Any	Yes	PD

**Evaluation overall**  
The best response is from the start treatment and imaging done weeks (± 7

6.2.5 **Response rate:** The clinical response rate is the percentage of evaluable patients who achieve complete response (CR) or partial response (PR) as the best overall response.

6.2.6 **Progression-free survival:** will be measured as the time from the start of pegylated liposomal doxorubicin to the time the patient is first recorded as having disease progression or dies. If a patient does not progress or die while being followed via tumor assessment, progression-free survival will be censored at the time of last disease assessment.

7. **Study Drug Information**

**Pegylated Liposomal Doxorubicin (Doxil)**

Doxil® (doxorubicin HCl liposome injection) is doxorubicin hydrochloride (HCl) encapsulated in STEALTH® liposomes for intravenous administration. Doxorubicin is a cytotoxic anthracycline antibiotic isolated from *Streptomyces peucetius* var. *caesius*. Doxorubicin HCl, is the established name for (8S,10S)-10-[(3-amino-2,3,6-trideoxy-β-L-lyxohexopyranosyl)oxy]-8-glycolyl-7,8,9,10-tetrahydro-6,8,11-trihydroxy-1-methoxy-5,12-naphthacenedione. Doxil will be obtained from commercial sources and administered on days 1 of 21 day cycle (this will be done as standard of care). This drug will be administered as directed by their package inserts or standard of care. Doxil will be administered intravenously at 30mg/m^2.

**Dose Modification Guidelines**

Patients will be carefully monitored for toxicity. Adverse reactions, such as Hand Foot Syndrome (HFS), hematologic toxicities, and stomatitis will be managed by dose delays and adjustments. Following the first appearance of a Grade 2 or higher adverse reactions, the dosing will be adjusted or delayed as described in the following tables. Once the dose has been reduced, it will not be increased at a later time. After a dose modification, if treatment is continued, it will return to the original dose interval of every 21 days.

**Recommended Dose Modification Guidelines**

**Table 1: Dose Adjustment for Hand-Foot Syndrome (HFS)**

Toxicity Grade	Dose Adjustment
1-mild erythema, swelling, or desquamation not interfering with daily activities	Redose unless patient has experienced previous Grade 3 or 4 HFS. If so, delay up to 2 weeks and decrease dose by 25%. Return to original dose interval.
2- erythema, desquamation, or swelling interfering with, but not precluding normal physical activities; small blisters or ulcerations less than 2 cm in diameter	Delay dosing up to 2 weeks or until resolved to Grade 0-1. If after 2 weeks there is no resolution, DOXIL should be discontinued. If resolved to Grade 0-1 within 2 weeks, and there are no prior Grade 3-4 HFS, continue treatment at previous dose and return to original dose interval. If patient experienced previous Grade 3-4 toxicity, continue treatment with a 25% dose reduction and return to original dose interval.
3- blistering, ulceration, or swelling interfering with walking or normal daily activities; cannot wear regular clothing	Delay dosing up to 2 weeks or until resolved to Grade 0-1. Decrease dose by 25% and return to original dose interval. If after 2 weeks there is no resolution, DOXIL should be discontinued.
4- diffuse or local process causing infectious complications, or a bedridden state or hospitalization	Delay dosing up to 2 weeks or until resolved to Grade 0-1. Decrease dose by 25% and return to original dose interval. If after 2 weeks there is no resolution, DOXIL should be discontinued.

**Table 2: Dose Adjustments for Stomatitis**

Toxicity Grade Dose Adjustment

1-painless ulcers, erythema, or mild soreness)	Redose unless patient has experienced previous Grade 3 or 4 HFS. If so, delay up to 2 weeks and decrease dose by 25%. Return to original dose interval.
2-painful erythema, edema, or ulcers, but can eat	Delay dosing up to 2 weeks or until resolved to Grade 0-1. If after 2 weeks there is no resolution, DOXIL should be discontinued. If resolved to Grade 0-1 within 2 weeks, and there are no prior Grade 3-4 HFS, continue treatment at previous dose and return to original dose interval. If patient experienced previous Grade 3-4 toxicity, continue treatment with a 25% dose reduction and return to original dose interval.
3-painful erythema, edema, or ulcers, and cannot eat	Delay dosing up to 2 weeks or until resolved to Grade 0-1. Decrease dose by 25% and return to original dose interval. If after 2 weeks there is no resolution, DOXIL should be discontinued.
4-requires parenteral or enteral support)	Delay dosing up to 2 weeks or until resolved to Grade 0-1. Decrease dose by 25% and return to original dose interval. If after 2 weeks there is no resolution, DOXIL should be discontinued.

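### Table 2 (stomatitis) carries over Table 1's hand-foot syndrome condition, so the grade 1 row keys on the wrong history and the grade 2 row is contradictory or ambiguous

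*Combined protocol and SAP*

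**What the plan says.** Section 7 starts pegylated liposomal doxorubicin at 30 mg/m² every 21 days. The Dose Modification Guidelines say that dosing will follow the tables once a grade 2 or higher reaction has appeared, and they make reductions permanent: "Once the dose has been reduced, it will not be increased at a later time".

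Table 2 covers stomatitis. The instructions that refer to the patient's history are:

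- Grade 1: "Redose unless patient has experienced previous Grade 3 or 4 HFS". If there is such a history, delay up to 2 weeks and reduce by 25%.
- Grade 2 that settles to grade 0-1 within 2 weeks, keep-the-dose sentence: if "there are no prior Grade 3-4 HFS, continue treatment at previous dose and return to original dose interval".
- Grade 2, reduction sentence: "If patient experienced previous Grade 3-4 toxicity, continue treatment with a 25% dose reduction".

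The grade 3 and 4 rows require a 25% reduction whatever the history. No row of Table 2 names earlier stomatitis. The grade 1 and grade 2 instructions match those of Table 1, the HFS table, where a condition on earlier HFS makes sense.

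**The concern.** Each of the two tables appears meant to treat a recurrence more cautiously after an earlier severe episode. Table 1 does this for HFS. Table 2 has the same structure, but its condition still points to HFS, which looks like text carried over without changing the toxicity.

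Two kinds of patient are affected. One has had severe stomatitis without severe HFS and should, on the evident logic of the table, be handled cautiously when stomatitis returns; at grade 1 the table does not do so. The other has had severe HFS and now has painless ulcers for the first time; the table delays this patient and lowers the dose for good because of a different toxicity.

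At grade 2 the wording is unclear as well, so the two enrolling centers could dose the same patient differently. This is a matter of dosing safety and of consistent treatment between sites.

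**Working it through.** There is no stated statistical figure to reproduce. The check is a row-by-row reading of Table 2 followed by the dose arithmetic.

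**Step 1. Apply Table 2 where the two histories differ.** With neither history, or with both, the choice of toxicity in the condition makes no difference.

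| Earlier grade 3-4 event | Stomatitis grade 1 now | Stomatitis grade 2 now, settled within 2 weeks |
|---|---|---|
| Stomatitis only | Redose on time, dose unchanged | Keep-the-dose sentence applies; reduction sentence also applies if 'toxicity' includes stomatitis |
| HFS only | Delay up to 2 weeks, cut 25% | Cut 25% if 'toxicity' includes HFS; no instruction if it means stomatitis alone |

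**Step 2. Read the grade 2 row for the stomatitis-only patient.**

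- If 'toxicity' means any toxicity, or stomatitis, one sentence keeps the dose and the next cuts it. The row contradicts itself.
- If 'toxicity' means HFS, as the context of Table 1 suggests, only the keep-the-dose sentence applies and the stomatitis history is ignored.

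Neither reading gives a sound instruction.

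**Step 3. Doses.** Inputs: starting dose 30 mg/m²; one 25% cut from the earlier grade 3 or 4 row; no re-escalation. Each cut is taken from the current dose.

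- After the earlier severe episode: 30 × 0.75 = 22.5 mg/m².
- After one further cut: 22.5 × 0.75 = 16.875, about 16.9 mg/m², or 16.875 / 30 = 56% of the starting dose.

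On recurrence at grade 1, the patient with earlier stomatitis stays at 22.5 mg/m² and is not delayed. A rule based on stomatitis history would delay and give 16.9 mg/m². The patient with earlier HFS and first mild stomatitis goes from 22.5 to 16.9 mg/m² permanently.

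The protocol does not say whether a second 25% is taken from the current or the starting dose. From the starting dose the second step would be 30 − 7.5 − 7.5 = 15.0 mg/m². The direction of the finding is the same.

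**The case against.** Several points on the other side have weight.

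- **The earlier episode was not ignored.** The grade 3 and 4 rows had already cut the dose by 25%, permanently. This stands, and it limits the loss to the further step on recurrence.
- **A reader might infer that both rows disregard stomatitis history outright.** That is too strong for grade 2, where 'toxicity' can be read to include stomatitis. The grade 2 fault is contradiction or ambiguity; only grade 1 is plainly wrong. It follows that the risk of differing doses between sites belongs to grade 2, since the grade 1 wording is clear.
- **HFS may have been meant to count.** No text says that stomatitis history alone should govern. If either history is meant to count, the cut after severe HFS is not an error. But a deliberate cross-toxicity rule would add HFS to stomatitis; it would hardly leave stomatitis out of its own table. The problem for the patient with earlier stomatitis therefore remains under either intention.
- **The tables are headed as recommended, and Section 7 also refers to package inserts or standard of care.** The guidelines nevertheless say that dosing will follow the tables, and nothing says which source prevails if they differ.

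A reader might also infer from Section 5.3 that patients can be re-treated unassessed, because the examination is due "No less than every 8 weeks" and blood tests "No less than every 4 weeks" while doses fall every 21 days. The documents do not support calling this an error. Those intervals are minimum frequencies, Section 7 calls for careful monitoring, and Tables 1 and 2 cannot be applied at redosing without grading the toxicity then.

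**Conclusion.** The point holds as a drafting error in a binding dosing table, and it should be corrected. At grade 1, Table 2 uses the wrong toxicity history without ambiguity. At grade 2, it is contradictory or ignores stomatitis history, depending on what 'toxicity' means.

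The size is one missed step for a patient whose stomatitis recurs after a severe episode: 22.5 instead of about 16.9 mg/m², and at grade 1 no delay. This assumes a starting dose of 30 mg/m², one earlier cut, and cuts taken from the current dose. That the patient with earlier HFS is over-reduced depends on a further assumption, that only stomatitis history was meant to count.

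The documents give no toxicity frequencies, so the number of patients affected cannot be estimated. A reader might infer some bias in the response rate through altered dose intensity; nothing in the documents allows that to be shown. The sample size and the two-stage design are untouched.

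**What to change.** In Table 2, replace 'HFS' with 'stomatitis' in the grade 1 row and in the grade 2 keep-the-dose sentence, and make the grade 2 reduction sentence use the same condition, so that the two grade 2 sentences are exact complements.

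The sponsor should choose the condition deliberately. Naming stomatitis alone removes reductions that the present text gives, or can be read to give, after severe HFS. If earlier severe HFS should also count, write 'HFS or stomatitis' in all three places.

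The cost is three wording changes in one short amendment. No procedure is added, and neither the sample size nor the analysis changes.

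### Table 2 (stomatitis) tests hand-foot syndrome history in its grade 1 and 2 rows, so earlier severe stomatitis is ignored at grade 1 and meets two opposite dose instructions at grade 2

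*Combined protocol and SAP*

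**What the plan says.** Section 7 (Study Drug Information) starts pegylated liposomal doxorubicin at 30 mg/m2 every 21 days. After a first adverse reaction of grade 2 or higher, "the dosing will be adjusted or delayed as described in the following tables", and a reduced dose is never raised again.

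Table 2 covers stomatitis.

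- Grade 1: "Redose unless patient has experienced previous Grade 3 or 4 HFS". With that history, the dose is delayed by up to 2 weeks and cut by 25%.
- Grade 2: every event delays dosing, and the drug stops if there is no resolution after 2 weeks. For events that do resolve, two sentences follow: "If resolved to Grade 0-1 within 2 weeks, and there are no prior Grade 3-4 HFS, continue treatment at previous dose", and then "If patient experienced previous Grade 3-4 toxicity, continue treatment with a 25% dose reduction and return to original dose interval".
- Grades 3 and 4: "Delay dosing up to 2 weeks or until resolved to Grade 0-1. Decrease dose by 25% and return to original dose interval". No history condition is attached.

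Table 1 covers HFS. Its grade 2 row has the same pair of sentences: "there are no prior Grade 3-4 HFS, continue treatment at previous dose and return to original dose interval" and "If patient experienced previous Grade 3-4 toxicity, continue treatment with a 25% dose reduction". The tables share the heading "Recommended Dose Modification Guidelines".

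**The concern.** The history condition in the first two rows of the stomatitis table appears to have been carried over from the HFS table without changing the name of the toxicity. Nothing in Section 7 gives a reason why dosing after mild stomatitis should turn on earlier severe HFS and not on earlier severe stomatitis.

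There are two separate faults. The grade 1 row is clear but looks at the history of a different toxicity. The grade 2 row uses HFS in one sentence and an undefined toxicity in the next, so one kind of patient falls under both.

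What is at stake is consistent dosing after a severe episode. Two centres dose from these tables, and a reduction cannot be reversed. Two clinicians who each follow the text could give the same patient different doses from then on.

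**Working it through.** The plan states no figure to reproduce, so the check is a case-by-case reading followed by short arithmetic.

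**Table 2 by history.** Severe means an earlier, separate grade 3-4 episode. Grade 2 events are taken to resolve to grade 0-1 within 2 weeks. Toxicity is read here as including stomatitis.

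| Severe history | Grade 1 stomatitis now | Grade 2 stomatitis now |
|---|---|---|
| Neither | Redose | Keep previous dose |
| HFS only | Delay and cut 25% | Cut 25% |
| Stomatitis only | Redose, no delay or cut | Keep **and** cut 25% |
| Both | Delay and cut 25% | Cut 25% |

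The third line holds both faults. At grade 1 it gets the same action as no severe history at all. At grade 2 the absence of severe HFS satisfies the first sentence, and the earlier severe stomatitis satisfies the second.

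**Does another reading of toxicity rescue the Table 2 grade 2 row?**

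- Any grade 3-4 toxicity: the conflict above.
- Stomatitis: the same conflict. A patient with severe HFS only would also meet neither sentence.
- HFS: no conflict, but earlier severe stomatitis then has no effect in either the grade 1 or the grade 2 row of the stomatitis table.

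No reading gives a rule that is both consistent and responsive to the toxicity being managed.

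**Table 1, grade 2 row.** With severe stomatitis only and grade 2 HFS now, the two sentences conflict if toxicity means any toxicity. They do not conflict if it means HFS. In a table about HFS the second reading is natural, so the ambiguity is mild.

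**Dose at stake after an on-study grade 3-4 episode.** The starting dose of 30 mg/m2 and the 25% step come from Section 7.

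- Unconditional first cut: 30 × 0.75 = 22.5 mg/m2.
- Further cut, 25% of the current dose: 22.5 × 0.75 = 16.875, about 16.9 mg/m2.
- Further cut, 25% of the starting dose: 22.5 − 0.25 × 30 = 15 mg/m2.

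Section 7 does not say which base applies. The two instructions therefore differ by 22.5 − 16.875 = 5.625, about 5.6 mg/m2 per dose, or by 22.5 − 15 = 7.5 mg/m2 per dose on the second base.

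**The case against.** The strongest reply is that this is a wording slip with little consequence. The grade 3 and 4 rows already cut the dose whatever the history, and that cut is permanent. The tables are headed as recommendations, and Section 7 also points to the package insert or standard of care. A careful clinician could take the more cautious sentence. A cross-toxicity rule may even have been intended.

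Much of this stands, and it sets the size of the point. It does not remove the point. The text above the tables says that dosing will follow them. Neither the heading nor the package-insert sentence says which of the two instructions prevails. A deliberate cross-toxicity rule would not explain why severe stomatitis counts for nothing at grade 1 in the stomatitis table.

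A reader might infer more than the documents support:

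- *That it is unclear when to delay.* It is not. The grade 2 delay applies to every event, and the grade 1 row is clear, although tied to the wrong history.
- *That Table 1 is equally contradictory.* Its conflict disappears if toxicity is read as HFS.
- *That patients stay on full dose after severe stomatitis on study.* They do not, because the first cut is unconditional.
- *That severe febrile neutropenia also triggers the grade 2 cut.* The word could literally cover it, but Table 3 gives it its own rule, and the point here does not depend on it.

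**Conclusion.** The point holds as a low-severity correction to a dosing table. In Table 2, earlier grade 3-4 stomatitis is ignored when grade 1 stomatitis appears, and it meets opposite instructions when grade 2 stomatitis appears in a patient without severe HFS. For on-study severe episodes the difference is one further step: 22.5 versus about 16.9 mg/m2 with the 25% taken from the current dose, or 15 mg/m2 with it taken from the starting dose.

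This rests on the earlier severe stomatitis being a separate episode and on the grade 2 event resolving within 2 weeks. For patients already on the drug at entry (Section 4.1.10), a severe episode may predate enrolment, and the tables do not say whether it counts. The documents give no frequency for any of these sequences, so the number of affected patients cannot be stated.

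A reader might go on to infer a bias in response rate or progression-free survival, or a safety failure from redosing at grade 1. The documents support neither. The grade 3 and 4 rows themselves accept redosing at grade 0-1, and nothing here touches the sample size, the two-stage rule or the error rates.

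**What to change.** Subject to clinical confirmation:

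1. Table 2, grade 1 row: replace *HFS* with *stomatitis*.
2. Table 2, grade 2 row: use *Grade 3-4 stomatitis* in both sentences.
3. Table 1, grade 2 row: for consistency, replace *toxicity* with *HFS* in the second sentence.

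This changes four phrases in two tables. It would help to add a sentence saying that the earlier episode must be a separate one. Otherwise a single severe episode that has settled to grade 1 could be cut under the grade 3-4 row and again under the amended grade 1 row.

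The downside is that patients with earlier severe HFS and new grade 1 or 2 stomatitis would no longer be cut on HFS history alone.

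If the investigator does intend a cross-toxicity rule, write *Grade 3-4 HFS or stomatitis* in all six places: the grade 1 row of each table, and both sentences of each grade 2 row. That keeps the present HFS-based cuts. It also adds a delay and a cut for grade 1 HFS or grade 1 stomatitis after severe stomatitis, where the text now says to redose, so it should be chosen knowingly.

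Either version is a short protocol clarification with no change to endpoints, sample size or analysis.
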